9.3 Secondary Endpoint(s)

The following secondary endpoints will be summarized in the same manner as the primary endpoint:

- proportion of subjects who completed colon cleansing
- proportion of subjects who completed the colonoscopy procedure
- proportion of subjects with responses to the individual questions on the Tolerability and Satisfaction Questionnaire

Additionally, based on the individual questions subjects responses will be categorized as tolerable and as satisfactory according to the following algorithms:

- Tolerable is defined as a response of 1 (Never) or 2 (Rarely) to the five items specified in question 3.
- Satisfactory is defined as a response of 1(Very Easy) or 2 (Easy) on question 1 and a response of 1 (Very Well) or 2 (Well) on question 2.

9.4 Pharmacokinetic Endpoints

For subjects that participated in the pharmacokinetic sub-study, the picosulfate and magnesium plasma concentrations will be summarized for the Prepopik treatment groups, overall and by age group. The summary will include the mean, median, standard deviation, minimum, maximum, coefficient of variation, geometric mean and geometric mean coefficient of variation. A listing of the concentration data will also be produced.

Analysis of the population pharmacokinetic endpoints is described in a separate document.

10 Safety

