#### **NUMBER OF SUBJECTS**

A sufficient number of subjects will be screened to ensure up to approximately 75 (for 9-12 years old, 15 subjects for the Prepopik ½ sachet x2, the Prepopik 1 sachet x2, and standard of care group; for 13-16 years old, 15 subjects for the Prepopik 1 sachet x2 and standard of care). For PK sampling, approximately 5 subjects per treatment group (a total of 15, 5 aged 13-16 years and 10 aged 9-12 years) will be assessed.

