Prepopik was first used in pediatrics in the United Kingdom in approximately 1980 and is currently used in several Western health arenas. Over 30 years' experience indicates that 12-18-year-old subjects respond well to the adult dosing. The current dosages used in pediatrics in the European Union for ages 9-18 years is 1 sachet (x2). In Canada, current pediatric dosage is ½ sachet (x2) for ages 9-12 years and 1 sachet (x2) for ages 13-18 years. This dosage has been studied in a well-controlled trial from the Toronto Hospital for Sick Children. It aimed to compare bowel preparation for colonoscopy in children with PicoSalax or PEG with electrolyte solution. Thirty five of PicoSalax patients (81%) were satisfied or very satisfied with the clean out compared with 19 (48%) in the PEG group (p=.001). Therefore, in our study, the younger group will compare adult dose (1 sachet x2 as in the European Union) and ½ the adult dose (1/2 sachet x2, Canadian dose). Pharmacokinetics will be evaluated to assess potential age-related differences in systemic exposure to major constituents (picosulfate and magnesium).

Trial Code: 000103 Date: 28-Jul-2014 E-Protocol Amendment-18395; Ver. 5

> Supersedes: 4 Page 16 of 65

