### 6.2 Randomization Visit (Visit 2)

The Randomization Visit (Visit 2) takes place  $\leq$  14 days from the Procedure (Visit 3). This visit may be combined with Visit 1 if all laboratory results are obtained prior to randomization.

If the study screening requirements, including positive laboratory results, are met:

- Urine pregnancy test (onsite) for adolescent female subjects of childbearing potential
- Measure orthostatic vital signs (blood pressure and pulse)
- Perform a directed physical examination
- Document any concomitant medications
- AEs (recorded by study personnel)
- Assign subject randomization number
- Dispense study medication
- Instruct the subject (and parent/guardian) how to self-administer the study medication and provide them with detailed information, complete with assigned times of drug administration

If the subject is participating in the PK subset, an additional laboratory sample will be obtained for baseline Mg ++. The baseline Mg ++ sample can be obtained at any time prior to IMP dosing.

> Supersedes: 4 Page 32 of 65

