# 7.3 Drug Concentration Measurements

For subjects that are participating in the PK subset, blood samples for measurement of picosulfate and magnesium plasma concentrations will be collected from approximately 15 subjects in the 3 Prepopik groups. Magnesium will be collected pre-dose at Visits 1, 2 or 3.). Picosulfate will be collected at Visit 3 (colonoscopy) in the (6-12 hour) window after the first dose of Prepopik. Sampling times at Visit 3 are at Hours 6, 8, and 12 for picosulfate concentrations and at Hour 10 for magnesium concentrations.

Analysis of the samples for sodium picosulfate and magnesium oxide will be performed by

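### SAP 9.4 reports PK-subset magnesium only as measured, with no change from the pre-dose value, so baseline differences can obscure or distort the non-randomized age comparison

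*SAP*

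**What the plan says.** Protocol 1.2 gives the reason for the PK work: to look at "potential age-related differences in systemic exposure to major constituents (picosulfate and magnesium"). Protocol 7.3 then sets two kinds of magnesium sample for the PK subset. The first is a baseline: "Magnesium will be collected pre-dose at Visits 1, 2 or 3". The second is a single post-dose time, "at Hour 10 for magnesium concentrations". Protocol 6.2 adds that at Visit 2 "an additional laboratory sample will be obtained for baseline Mg", and the notes to Table 6-1 let the baseline be drawn at any time before dosing. The synopsis plans "approximately 5 subjects per treatment group (a total of 15, 5 aged 13-16 years and 10 aged 9-12 years").

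On the analysis, SAP 9.4 states that "the picosulfate and magnesium plasma concentrations will be summarized for the Prepopik treatment groups, overall and by age group". Besides the mean, median, SD and range, it lists "coefficient of variation, geometric mean and geometric mean coefficient of variation", and it promises a listing of the concentrations. It refers the population PK analysis to a separate document. SAP 1.1 defines change from baseline, and SAP 10.3.1 and 10.4.1 use it for laboratory values and vital signs. SAP 9.4 does not use it.

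**The concern.** Picosulfate comes only from the drug, so its measured concentration reflects exposure. Magnesium does not: a measured value at Hour 10 is the child's own magnesium plus whatever the preparation added. A pre-dose sample is the natural means of separating the two, and the protocol takes one, but SAP 9.4 never pairs it with the Hour 10 value.

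This matters most for the stated question. Children aged 9-12 and 13-16 are not randomized to their age, so nothing balances baseline magnesium between them. If the age groups differ before dosing, the table of measured values will show that difference as though it were a difference in exposure, or will hide a real one. With so few children per group, variation in baseline between children also adds noise. What is at stake is how far a secondary PK description can be interpreted. No decision rule depends on it.

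**Working it through.** **Plan's own figure.** The documents give no precision figure for the PK subset. Their only one is the efficacy interval (45 subjects, 80% success, 65% - 90%). The exact interval for 36/45 is 65.4% to 90.4%, so it reproduces, but it has no bearing here.

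**Step 1: what enters each comparison.** Write a child's Hour 10 value as Y = B + R, with B the pre-dose magnesium and R the rise.

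- Age comparison, same dose: E(Y, older) - E(Y, younger) = [E(B, older) - E(B, younger)] + [E(R, older) - E(R, younger)]. The first bracket need not be zero. Subtracting the pre-dose value removes it.
- Dose comparison at ages 9-12: randomization makes E(B) equal in the two dose groups, provided entry to the PK subset does not depend on magnesium status. Then E(Y, 1 sachet) - E(Y, 1/2 sachet) = E(R, 1 sachet) - E(R, 1/2 sachet), with no bias.

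**Step 2: check of the dose comparison by simulation.** Assumed values in arbitrary units: baseline mean 1 and SD 0.10; rises 0.10 and 0.20, each with SD 0.05; 5 per group; 200,000 repeats.

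- Measured values: mean difference 0.100, SE 0.071. By formula, √(2 × (0.10² + 0.05²)/5) = √0.005 = 0.071.
- Change: mean difference 0.100, SE 0.032. By formula, √(2 × 0.05²/5) = √0.001 = 0.032.

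Both centre on the true difference. Change is tighter here because the assumed pre/post correlation is high, at 0.10/√0.0125 = 0.89.

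**Step 3: precision over the whole range of correlation.** With equal pre and post SD, SD(change)/SD(raw) = √(2(1 - r)). With 5 per group, the approximate 95% half-width of a difference between two groups is 1.96 × √(2/5) = 1.24 raw SD for measured values, and that figure times the SD ratio for change.

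| r | SD ratio | Half-width, change (raw SD) | Half-width, measured (raw SD) |
|---|---|---|---|
| 0 | 1.41 | 1.75 | 1.24 |
| 0.3 | 1.18 | 1.47 | 1.24 |
| 0.5 | 1.00 | 1.24 | 1.24 |
| 0.7 | 0.77 | 0.96 | 1.24 |
| 0.9 | 0.45 | 0.55 | 1.24 |

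The documents do not give r. By Table 6-1 the baseline may date from Visit 1, up to 42 days before colonoscopy, so a low r cannot be ruled out.

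**Step 4: ratios, as illustration only.** Let f be the full-dose rise as a share of baseline, and assume that half the dose gives half the rise. The ratio of measured values is then (1 + f)/(1 + f/2). For f = 10%, 20%, 30%, 50% and 100% it is 1.05, 1.09, 1.13, 1.20 and 1.33, where the ratio of the rises is 2.0. SAP 9.4 plans no ratios, so this concerns only a reader who forms one from the table.

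**The case against.** Four arguments deserve weight.

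*The laboratory tables already give change in magnesium.* Serum magnesium is in the chemistry panel at Visits 1, 3 and 4 (Protocol 7.2.3), and SAP 10.3.1 reports change from baseline by treatment and age group. That covers about 45 Prepopik subjects and a standard-of-care reference, against 15 in the PK subset. It is drawn when completion of treatment is checked. Hour 10 is at most 4 hours after the second split dose (10 - 6 = 4, from Protocol 5.1) and may precede it. This stands as a partial substitute. The Visit 3 sample, however, is run at a local laboratory, has no fixed time after dosing, and is not the Hour 10 PK sample.

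*The population PK document may model baseline.* It may; it is not available, so this cannot be checked. It would not alter the table in SAP 9.4. A reader might infer that the trial never adjusts magnesium for baseline. The documents support that statement for SAP 9.4 only.

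*Pre-dose values may already appear in the 9.4 table or listing.* The SAP does not exclude them. With complete pairs, mean change would equal the difference of the two means. The SD and range of change still need the within-child pairing, which two separate rows do not give. A listing with both values would let a reader derive them.

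*Change is not sure to be more precise.* This is correct, and it is the reason to show both.

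**Conclusion.** The gap is real but small. SAP 9.4 has a pre-dose and an Hour 10 magnesium value for each child in the PK subset and summarizes concentrations without pairing them. Baseline differences between children can therefore obscure the comparison, and baseline differences between age groups can distort it. The age comparison is the stronger ground, because it is the stated purpose and is not randomized. This rests on one assumption: that the Hour 10 value is the sum of endogenous magnesium and a rise.

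A reader might infer that the body's own magnesium masks the dose effect, or dominates the summary. The documents do not support this. They give no endogenous level, SD, rise or correlation, and say only that levels rose transiently in adults. The dose difference in means at ages 9-12 is unbiased. Diluted ratios concern a statistic that the SAP does not plan, and Protocol 1.2 names age differences, not dose differences, as the purpose. Picosulfate is unaffected.

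The size of any distortion cannot be derived from the documents. The endpoint is secondary and descriptive, so this is a desirable improvement and not a flaw that threatens the trial's conclusions.

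**What to change.** In SAP 9.4, add change from pre-dose baseline for Hour 10 magnesium (n, mean, SD, median and range), by Prepopik group and age group, beside the measured concentrations. Use the baseline definition already in SAP 1.1. Add one sentence saying whether the separate population PK document models baseline magnesium.

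The cost is one block in an existing table: no new samples and no change to trial conduct. The one downside is that change is noisier than the measured value when the within-child correlation is below 0.5. Keeping both columns covers that case.

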10.1 General Considerations

Safety parameters will be evaluated for the safety analysis data set. Subjects will be summarized by actual treatment received.

10.2 Adverse Events

All AEs will be coded using MedDRA version 16.1 or later. The relation between AEs and study medication will be characterized as having a reasonable possibility or not. The intensity of AEs will be characterized as mild, moderate, or severe.

Treatment-emergent AEs are those adverse events which begin after the start of study treatment or which worsen after the start of study medication. Any event with partial date information reported on or after the date of the first dose of study treatment will be considered treatment-emergent. Only treatment-emergent AEs will be summarized.

Written narratives will be issued for all serious AEs (including deaths) and AEs leading to withdrawal.

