# 6.3 Procedure/Colonoscopy Visit (Visit 3)

The Procedure Visit (Visit 3) takes place  $\leq$  42 days from Visit 1.

Before colonoscopy, the following will be performed/recorded/checked:

- Treatment completed
- Perform a directed physical examination
- Acceptability and tolerability questionnaire completed by subject or parent/guardian
- Obtain vital signs
- Obtain laboratory sample: chemistry, hematology, coagulation
- Urinalysis
- AEs (recorded by study personnel)
- Document any concomitant medications
- Perform study drug accountability
- If the subject is participating in the PK subset, laboratory samples will be obtained at Hours 6, 8, 10 and 12 after first dose

The subject or parent/guardian should be instructed to fill out the questionnaire during the visit in a private area prior to contact with the investigator and return the completed questionnaire to the study coordinator. If the coordinator is not available during the procedure, the subject/parent or guardian will place the completed questionnaire in a sealed envelope and provide it to a member of the surgical team. The study coordinator should check each questionnaire for completion and, if the subject did not answer all/some of the questions, note the reasons on the first page of the questionnaire. No one (including study coordinator or a family member or guardian) should interpret questions or response choices for the subject.

During the colonoscopy procedure, the blinded gastroenterologist will use the Aronchick Scale to score the quality of the bowel preparation of the study drug for overall colon cleansing and record the outcome of the colonoscopy.

Post-colonoscopy, the following will be performed/recorded/checked:

- AEs (additional to those recorded prior to colonoscopy)
- Measure orthostatic vital signs (blood pressure and pulse)

Trial Code: 000103 Date: 28-Jul-2014 E-Protocol Amendment-18395; Ver. 5

Supersedes: 4 Page 33 of 65

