# 6.4 Follow-up Visits (Visits 4 and 5)

During Visit 4 (5 ( $\pm$ 2) days after colonoscopy), the following will be obtained:

- AEs
- Document any concomitant medications
- Obtain laboratory sample: chemistry, hematology and coagulation
- Urinalysis
- Measure orthostatic vital signs (blood pressure and pulse)

During Visit 5 (28  $[\pm 5]$  days after colonoscopy), the investigator or coordinator will interview the subject or parent/guardian via phone about any changes in concomitant medications, concomitant illness, or any new illnesses since the last visit. New illnesses or worsening in concomitant illnesses should be reported as AEs.

Trial Code: 000103

Date: 28-Jul-2014 E-Protocol Amendment-18395; Ver. 5

Supersedes: 4 Page 34 of 65

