#### 8 ADVERSE EVENTS

#### **Adverse Event Definition** 8.1

An AE is any untoward medical occurrence in a subject participating in a clinical trial. It includes:

- Any unfavorable and unintended sign, symptom or disease temporally associated with the use of the IMP, whether or not considered to be caused by the IMP
- AEs commonly observed and AEs anticipated based on the pharmacological effect of the IMP
- Any laboratory abnormality, vital sign or finding from physical or gynecological examination assessed as clinically significant by the investigator (note: findings from assessments and examinations done during screening are not AEs, but are recorded as medical history.)
- Accidental injuries, reasons for any change in medication (drug and/or dose), reasons for any medical, nursing or pharmacy consultation, or reasons for admission to hospital or surgical procedures
- Overdoses and medication errors with and without clinical consequences

An adverse drug reaction (ADR) is an AE evaluated by the investigator as being probably or possibly causally related to treatment with the IMP.

A serious ADR is an SAE evaluated by the investigator and/or by Ferring as being probably or possibly causally related to treatment with the IMP (further described in Section 8.2.2).

An unexpected AE is an AE not identified in nature, severity, or frequency in the section "Undesirable Effects" in the sponsor's current Investigator's Brochure and current approved label.

A treatment-emergent AE is any AE that begins during the treatment period, or is a worsening of a pre-existing medical condition. The treatment period is the period during which a subject receives IMP.

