# **8.2.2** Recording of Adverse Events

The investigator must record all AEs in the Adverse Event Log provided in each subject's CRF with information about the:

- AE
- Date and time of onset (time can be omitted, if applicable)
- Intensity
- Causal relationship to IMP
- Action taken to IMP
- Other action taken
- Date and time of outcome (time can be omitted, if applicable)
- Outcome
- Seriousness

Each of the items in the Adverse Event Log is described in detail in the following sections.

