1.1 Definitions/ Abbreviations

Terms	Definitions
Analysis set	Data included in a specific analysis
Aronchick Scale	see Protocol section 7.1
Baseline	The last observed value collected prior to the start of treatment
Change from baseline	Difference between a data value at an analysis time point minus the corresponding baseline value
Concomitant medications	Medication taken during the study
Percent change from	Numerical percent difference between baseline value and post-
baseline	baseline value at a given study visit
Preparation	In this study, this term and the term "treatment," which is generally used in clinical trials, may be used interchangeably
Prior medications	Medications taken before entering the study
Randomization	The unpredictable allocation of a subject to a particular treatment (or preparation) in a clinical trial
Randomized	Subject randomized to trial treatment
Responder	A responder will be defined for the Aronchick Scale as subject rated as excellent or good during the colonoscopy
Screened	Subject who enters Screening
Screening	Questions and assessments performed to determine if a person qualifies to enter a clinical trial
TEAE	Any adverse event that occurs during or after the start of
	treatment or begins prior to preparation and increases in intensity during and/or after the start of preparation

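### SAP 10.2 sets no end to the treatment-emergent AE window and no split by onset, so AE incidence mixes preparation, procedure and later illness; the change from protocol 8.1 is not declared

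*SAP*

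**What the plan says.** **SAP.** Section 10.2 states: "Treatment-emergent AEs are those adverse events which begin after the start of study treatment or which worsen after the start of study medication". The SAP glossary (1.1) is equally open; its entry starts "Any adverse event that occurs during or after the start of" treatment and names no last day. Section 10.2 adds: "Only treatment-emergent AEs will be summarized". This definition therefore decides what enters every AE incidence table. SAP 10.2.1 and 10.2.2 break these events down by system organ class and preferred term, maximum intensity, relationship, seriousness, withdrawal and death. Neither section uses time of onset or the colonoscopy as a divider.

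**Protocol.** Section 8.1 reads: "A treatment-emergent AE is any AE that begins during the treatment period, or is a worsening of a pre-existing medical condition". It continues: "The treatment period is the period during which a subject receives IMP". Section 9.8.2 promises incidence tables of treatment-emergent AEs, so 8.1 defines a protocol-specified analysis.

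**Collection.** AEs are followed from consent to the last visit (protocol 8.2.1). That visit is a call 28 (±5) days after colonoscopy, for which section 6.4 says: "New illnesses or worsening in concomitant illnesses should be reported as AEs". At Visit 3, section 6.3 lists AE recording once before and once after the procedure. Section 8.2.2 asks for onset date and time but lets the time be left out.

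**Declared changes.** SAP 12 lists three: added 90% intervals, orthostatic summaries and PK concentration summaries. The treatment-emergent definition is not among them.

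**The concern.** A secondary objective is to describe the safety of Prepopik. The preparation is taken over a short period and is followed directly by sedation and colonoscopy, in children who have a reason to be scoped. Protocol 1.3 names vomiting, diarrhea, nausea and abdominal pain as the commonest reactions to the product. Sedation, the procedure and the underlying condition can plausibly produce the same terms. A table with one open window cannot show which part of the incidence belongs to which period.

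The two definitions also fail in opposite directions. Read literally, protocol 8.1 omits a new reaction that begins after the last dose, even before colonoscopy. SAP 10.2 captures it, but also captures an unrelated illness three weeks later. The SAP replaced one rule with the other without saying so. It does bound treatment-emergent laboratory and vital-sign data by residual drug effect (10.3, 10.4), although it gives no length for that, and it sets no bound at all for AEs.

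**Working it through.** The plan states no AE rate and no window length, so there is no figure of its own to reproduce on this point. Three checks follow.

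**1. Length of the window (split-dose Prepopik).**
- Inputs from protocol Table 6-1, note f: first dose 17:00 to 21:00 on the day before; second dose at least 6 h later and 5 to 9 h before colonoscopy.
- Visit 5 is 23 to 33 days after colonoscopy.
- Assumption: colonoscopy starts between 07:00 and 17:00.
- Shortest lead-in: colonoscopy 07:00, second dose 02:00, first dose 20:00, so first dose to colonoscopy is 11 h.
- Longest lead-in: first dose 17:00, colonoscopy 17:00 next day, so 24 h.
- Dose to dose: at least 6 h by rule; at most 17:00 to 12:00 next day, 19 h.
- Share of the SAP window before colonoscopy = lead-in / (lead-in + 24 × follow-up days). Lowest: 11 / (11 + 24 × 33) = 11/803 = 1.4%. Highest: 24 / (24 + 24 × 23) = 24/576 = 4.2%.

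These are shares of calendar time, not of events. They do not cover the Day Before option, whose first dose may be in the afternoon (protocol 5.1), or standard of care, whose duration is left to label or institution.

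**2. What a later background risk would do (illustration only).** Let p be the risk of any AE in the preparation period and b an independent later risk, equal in both arms. The risk of any TEAE is 1 − (1 − p)(1 − b), so the risk difference shrinks by the factor (1 − b). Taking p = 20% and 40% as assumed values:

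| b | any TEAE | difference | ratio |
|---|---|---|---|
| 0 | 20% vs 40% | 20 points | 2.00 |
| 10% | 28% vs 46% | 18 points | 1.64 |
| 20% | 36% vs 52% | 16 points | 1.44 |
| 40% | 52% vs 64% | 12 points | 1.23 |
| 60% | 68% vs 76% | 8 points | 1.12 |

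The net number of children added in an arm of 15 is 15 × (1 − p) × b:
- p = 20%: 15 × 0.8 × 0.2 = 2.4 when b = 20%; 15 × 0.8 × 0.4 = 4.8 when b = 40%.
- p = 40%: 15 × 0.6 × 0.2 = 1.8 and 15 × 0.6 × 0.4 = 3.6.

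None of these rates is in the documents.

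**3. An effect that needs no assumed rate.** SAP 10.2.2 tabulates non-serious AEs reaching 5% in any treatment group. The ½-sachet arm has 15 children, and 1/15 = 6.7%. One minor illness first reported at the Day 28 call is enough to enter that table.

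**The case against.** The strongest reply is that counting every event to the end of follow-up is conservative, that safety here is descriptive with no hypothesis, and that other outputs already isolate the preparation. Much of this stands.

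- **Related events.** SAP 10.2.1 and 10.2.2 tabulate adverse drug reactions and AEs by relationship. One might discount these because subject and coordinator know the treatment. However, the investigator judges causality, and protocol 3.5.3 and 6.3 point to an investigator meant to stay blinded (emergency envelope; questionnaire completed before contact with the investigator). The remaining weakness is overlap of symptoms.
- **Questionnaire.** It is completed before sedation, and SAP 9.3 summarizes each item. It isolates abdominal pain, fullness, night waking, nausea and bother from toilet visits. It does not ask about vomiting and does not replace AE terms.
- **Preferred terms and listings.** A later unrelated illness appears under its own term, and all AEs are listed.
- **Table shells.** They are in a separate document (SAP 14) and may contain a split. The SAP text does not provide for one.

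Four stronger readings are tempting, and the documents do not support them.

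- *The comparison with standard of care is biased.* The open-ended rule is the same in all arms; it dilutes rather than favors.
- *The protocol definition stops entirely with IMP intake.* Only its new-onset limb does. Worsening of a pre-existing condition has no time limit, so later worsening of the underlying disease counts under both documents.
- *A definite number of extra children per arm can be stated.* No background rate is given, and a child who already has a preparation-period event is not added again.
- *First dose to colonoscopy should be the main safety table.* Protocol 1.1 gives picosulfate 6 to 10 h to act, and the second dose may be 5 h before the procedure. Its action can therefore start 6 − 5 = 1 h to 10 − 5 = 5 h after the colonoscopy begins. Protocol 1.3 reports adult laboratory shifts and raised magnesium resolving 24 to 48 h after the procedure. Such a main table would lose real preparation effects.

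**Conclusion.** The point holds in moderate form. The SAP window has no end, collection runs to the Day 28 (±5) call, the SAP describes no AE table split by onset, and the departure from protocol 8.1 is not declared in SAP 12. The between-arm comparison is not biased. Incidence will be higher than that of the preparation alone, and any difference will be diluted by (1 − b) if the later risk b is independent and equal across arms. The documents do not give b, so the size is unknown. The 1.4% to 4.2% share describes time only, applies to split-dose Prepopik, and rests on the assumed colonoscopy hours. Related-AE tables and the questionnaire limit the damage without removing it. Neither definition is adequate alone: the protocol's is too narrow for new events, and the SAP's is too wide to describe the preparation without a split.

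**What to change.** 1. Keep the SAP total TEAE table as the main table.
2. Add to SAP 10.2.2 a TEAE table by onset period: first dose to start of colonoscopy; start of colonoscopy to Visit 4; after Visit 4. Add a note that preparation effects can also appear in the second period.
3. Require AE onset time for events from first dose through Visit 3. Site records are already taken before and after the procedure, but an event dated to the procedure day with no time may not be assignable to a period.
4. Reconcile protocol 8.1 with SAP 10.2, state the last day of the window explicitly, and list the change in SAP 12. SAP 7.3 refers to a visit 6, which the protocol does not have; correct this at the same time.

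The cost is one more table, small counts per cell with 15 children per arm, and mandatory onset time on the dosing and procedure days. No visit is added and no planned total is lost.
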